9.5. Efficacy

9.5.1. Efficacy Endpoints

9.5.1.1. Primary Efficacy Endpoint

The primary efficacy endpoint is the overall response rate within each cohort, defined as the percentage of subjects achieving serum 17-OHP targets as follows:

- Men and postmenopausal women: 17-OHP \leq 2x ULN
- Premenopausal women:

- Follicular phase: $17\text{-OHP} \leq 2x$ follicular phase ULN
- Luteal phase: $17\text{-OHP} \leq (2x \text{ follicular phase ULN} + (\text{luteal phase ULN} - \text{follicular phase ULN}))$

9.5.1.2. Secondary Efficacy Endpoints

The secondary efficacy endpoints will be defined in the SAP. There are no prespecified efficacy targets for the secondary efficacy endpoints.

9.5.2. Efficacy Analysis Methodology

9.5.2.1. Analysis of the Efficacy Endpoints

Only observed case data will be used for the efficacy summaries. The levels of adrenal steroids, steroid intermediates, and other measured hormones will be summarized for the mITT and PP populations using descriptive statistics, including number of non-missing observations (n), mean and/or median, standard deviation (SD) and/or percentiles, minimum (min), maximum (max) and 90% confidence intervals, if applicable. The analysis will be performed by value and by change from baseline in the value, where appropriate, for each time point, overall, by nevanimibe HCl dose, and by cohort. The percentage of subjects achieving serum 17-OHP targets, the primary endpoint, will be summarized overall and by cohort. The study will be considered positive if 40% or more of enrolled subjects in either cohort achieve the primary endpoint.

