3.1.2. Baseline Period

At the Baseline Visit (Visit B1), additional laboratory tests will be done as part of study eligibility. In addition, subjects will be instructed on the use of an electronic diary (eDiary) for recording their glucocorticoid, mineralocorticoid (if applicable), and study drug doses (and, for premenopausal women, start dates of menstrual periods) during the study. The most recent serum 17-OHP level should be $\geq 4x$ ULN for all subjects prior to Visit B1. Any subject whose Visit B1 serum 17-OHP is $< 4x$ ULN should be discussed with the Medical Monitor prior to enrolling in the study. Cohort 2 subjects may require further decreases in glucocorticoid dose and subsequent assessment of serum 17-OHP during the Baseline Period (see Appendix 2). No study drug will be given during the Baseline Period. The Baseline Period may last from approximately 2-8 weeks.

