4.2. Inclusion Criteria

Each subject must meet all the following criteria to be enrolled in this study:

1. Provision of signed and dated informed consent prior to any study-specific procedures
2. Men and women 18 to 80 (70 in the Czech Republic) years of age (inclusive) at the time of informed consent
3. Documented historical diagnosis of classic CAH due to 21-hydroxylase deficiency based on either or both of the following criteria:
 - Documented genetic mutation in the CYP21A2 enzyme consistent with a diagnosis of classic CAH
 - Historical documentation of elevated 17-OHP (e.g., in infancy or following a cosyntropin/ACTH stimulation test)
4. Serum 17-OHP \geq 4x ULN during the Baseline Period
 - Premenopausal women in the follicular phase of the menstrual cycle must have serum 17-OHP \geq 4x follicular phase ULN
 - Premenopausal women in the luteal phase of the menstrual cycle must have serum 17-OHP \geq (4x follicular phase ULN + (luteal phase ULN – follicular phase ULN))
5. Chronic glucocorticoid replacement therapy for at least 6 consecutive months prior to Screening
6. Stable glucocorticoid and mineralocorticoid regimen for at least 4 weeks prior to the Screening (S1), Baseline (B1), and Enrollment (T1) Visits
7. For subjects who undergo maintenance glucocorticoid dose adjustment between Screening and Enrollment, stable serum 17-OHP levels (adjusted as needed for menstrual cycle phase) prior to Enrollment, defined as the most recent 2 values being within 30% of each other (calculated as $100 \times (1 - (\text{smaller value}/\text{larger value}))$)
8. Female subjects of childbearing potential must consent to use two medically acceptable methods of contraception, excluding depot progesterone, throughout the study period and for 30 days after the last dose of study treatment during any sexual intercourse with a fertile male partner (in France: Fertile subjects (male and female) must consent to use two medically acceptable methods of contraception, excluding depot progesterone, throughout the study period and for 30 days after the last dose of study treatment during any sexual intercourse with a fertile partner of the opposite sex)

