7.2.2. After Visit B1

Within 2 weeks after Visit B1, prior to Visit T1, review serum 17-OHP results (see Appendix 2):

- If 17-OHP is $\geq 4x$ ULN:
 - If the subject met criteria for Cohort 1 based on the S1 serum 17-OHP, the subject should return for the Enrollment visit, Visit T1, as scheduled.
 - If the subject met criteria for Cohort 2 based on the S1 serum 17-OHP, assess stability of 17-OHP.
 - For the purposes of this study, “stable” serum 17-OHP levels following a glucocorticoid dose reduction are defined as the most recent two 17-OHP levels prior to enrollment being within 30% of each other (calculated as $100 \times (1 - (\text{smaller value}/\text{larger value}))$).
 - If 17-OHP levels are stable, the subject should return for the Enrollment visit, Visit T1, as scheduled.
 - If 17-OHP levels are not stable, discuss the case with the Medical Monitor, and consider obtaining a repeat serum 17-OHP level(s). Once the repeat 17-OHP levels are $\geq 4x$ ULN and meet stability criteria, the subject may proceed to the Enrollment visit, Visit T1.

- If 17-OHP is $< 4x$ ULN:
 - If the subject met criteria for Cohort 2 based on the S1 serum 17-OHP, assess the subject's maintenance glucocorticoid replacement dose in equivalent mg of hydrocortisone/m² body surface area (see Appendix 3) and discuss the case with the Medical Monitor.
 - If ≥ 12 mg/m², with agreement of the Medical Monitor, it may be possible to reduce the dose by the equivalent of approximately 5 mg hydrocortisone or 1 mg prednisone or prednisolone. The subject should then return for an Unscheduled visit at least 2 weeks after the dose change to assess 17-OHP levels. Further management should be discussed and agreed with the Medical Monitor.
 - If < 12 mg/m², discuss the case with the Medical Monitor.
 - In the unlikely event that a subject in Cohort 1 (based on the S1 serum 17-OHP), has 17-OHP $< 4x$ ULN, discuss the case with the Medical Monitor.

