3.2 Coding Systems and Conventions

3.2.1 Definition of Baseline

In general, all values recorded at Visit T1 (Day 1) prior to the first dose will be regarded as baseline values for this study. In case no predose Visit T1 (Day 1) value was recorded (expected for ECG and for coagulation parameters), the most recent value prior to Visit T1 (Day 1) will be used as baseline value instead.

For serum or plasma 17-OHP, P, cortisol, A4, ACTH, total T, and 11-ketoT, baseline is defined as the mean of the predose value from Visit T1 (Day 1) and the most recent “0-hour” value prior to Visit T1 (Day 1), if the glucocorticoid dose was the same as at Visit T1 (Day 1) (if not the same, then only the predose Visit T1 (Day 1) value will be used).

For on-site salivary 17-OHP, P, and cortisol, baseline is defined as the mean of the predose value from Visit T1 (Day 1) and the most recent “0-hour” value prior to Visit T1, if the glucocorticoid dose was the same as at Visit T1 (if not the same, then only the predose Visit T1 value will be used). Change from baseline will be calculated for salivary 17-OHP values obtained 30 minutes before, as well as 2 hours and 4 hours after intake of the morning dose of nevanimibe HCl. For additional analyses, baseline for on-site salivary 17-OHP is further categorized by the time of sample relative to the time of the morning dose of nevanimibe HCl. Thus, baseline for the predose measurement on visits T2/T3/T4/T5 is defined for the additional analyses as above, while it is defined as the T1 sample taken 2 hours after the morning dose of nevanimibe HCl for the T2/T3/T4/T5 sample taken 2 hours after the morning dose, and defined as the T1 sample taken 4 hours after the morning dose for the T2/T3/T4/T5 sample taken 4 hours after the morning dose.

For home collection salivary 17-OHP profiles, baseline for the 8 AM (08:00), noon (12:00), 4 PM (16:00), 8 PM (20:00), and 10-11 PM (22:00-23:00) time points is defined as the value obtained for the corresponding time point at Day -8.

Except for the above-mentioned case, all values recorded after the first treatment with the study drug will be regarded as post-baseline values.

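### The SAP's two-visit baseline for serum 17-OHP includes a value selected for being at least 4x ULN and conflicts with the Visit T1 reference elsewhere in the SAP; a small fall can appear without drug effect

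*Protocol*

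**What the plan says.** Protocol 9.5.2.1 asks for summaries of value and of change ("The analysis will be performed by value and by change from baseline in the value, where appropriate, for each time point") but does not define baseline. SAP 3.2.1 does so for serum 17-OHP: "baseline is defined as the mean of the predose value from Visit T1 (Day 1) and the most recent" 0-hour value before T1. The earlier value is dropped if the glucocorticoid dose differed from that at T1. In practice the earlier value is B1 or a repeat of it.

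That value is also the entry test. Protocol 4.2, criterion 4, requires serum 17-OHP of at least "4x ULN during the Baseline Period", adjusted for cycle phase, in both cohorts. The test is not absolute: Protocol 3.1.2 says that a subject with a lower B1 value "should be discussed with the Medical Monitor prior to enrolling in the study". Subjects whose glucocorticoid dose was adjusted need stable levels as well, "defined as the most recent 2 values being within 30% of each other" (criterion 7). Protocol 7.2.2 allows repeat sampling: once repeat levels are high enough and "meet stability criteria, the subject may proceed to the Enrollment visit, Visit T1".

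The T1 predose value plays no such part. It is drawn at the visit where dosing starts (Protocol 7.3.1), and Protocol 3.1.3 gives about 10 days for a 17-OHP result.

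Two other places in the SAP use a different reference. Section 6.3 names Visit T1 as the baseline for the serum 17-OHP change, and 7.6 compares the summed 0-4 h series with Visit T1.

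**The concern.** A value kept only if it clears a threshold overstates the subject's usual level on average when that level is close to the threshold. Here such a value makes up half of the baseline, while the values at T2 to T5 are not selected. In a single-arm trial nothing subtracts the difference, so part of an apparent fall in 17-OHP could be regression to the mean.

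At stake is how the size of effect on 17-OHP is described, above all for Cohort 2. Its subjects enter screening below 4x ULN and are raised to that level by glucocorticoid reduction, so they are plausibly nearer the threshold than Cohort 1. Because the SAP names two references, the reported change also depends on which one the programmer follows.

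**Working it through.** The documents give no within-subject variation, no expected change and no formal sample size calculation, so there is no planned figure to reproduce. The check is a simulation with no drug effect.

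**Inputs from the plan.** Entry: last two values at least 4x ULN and, in Cohort 2, smaller/larger at least 0.70. Baseline = (B1 + T1)/2. Percentage change = (Day x - baseline)/baseline (SAP 7.6). T1 is not used for entry.

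**Assumed inputs.** Cohort 2: true level after glucocorticoid reduction log-normal, median 3.5-6x ULN, between-subject log-SD 0.4; within-subject log-SD 0.3-0.5; independent visit errors. Cohort 1: median 30x, log-SD 1.0. The only anchor is Protocol 3.2: mean 53x ULN, range 7-187x, in the earlier study's Cohort 1-like subjects.

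**Step 1, selection.** In Cohort 2, B1 exceeds T1 by a geometric-mean ratio of 1.04 to 1.28. Half of this enters a log-scale baseline: 1/sqrt(1.04) = 0.98 and 1/sqrt(1.28) = 0.88, a fall of 2-12%. In Cohort 1 the B1/T1 ratio is 1.004-1.013 and the fall is under 1%. SAP 7.1 provides geometric means only for PK data, so this is not a planned statistic.

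**Step 2, Cohort 2 on arithmetic-scale statistics, no drug effect.**

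| Statistic | Two-visit baseline | T1 alone |
|---|---|---|
| Mean change / mean baseline | -0.3% to -6.4% | 0% |
| Mean of individual percentage changes | about -1% to +7% | +9% to +28% |
| Median percentage change | -4% to -16% | 0% |

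**Step 3, the part not due to selection.** With no entry threshold at all, the median percentage change from the two-visit mean is still about -2% to -6%. The log of an arithmetic mean of two values exceeds the mean of their logs by roughly (log-SD)^2/4: 0.3^2/4 = 0.0225 and 0.5^2/4 = 0.0625. The T1-only mean percentage is inflated for a related reason: exp(0.3^2) - 1 = 9% and exp(0.5^2) - 1 = 28%.

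**Step 4, sensitivity (mean change / mean baseline, Cohort 2 unless stated).** Within-subject CV 20-60% unless given.
- True median 3x, log-SD 0.3: -3.6% to -13.4%. Median 4x, log-SD 0.5: -0.8% to -3.6%. Median 6x, log-SD 0.6: -0.1% to +0.6%. Median 10x, log-SD 0.8: +0.2% to +2.8%.
- Stability rule (median 4x, CV 40%): -2.1% with it, -4.0% without. Two repeats change results by less than 1 point.
- 17-OHP still rising 5-20% per visit interval before T1 (median 6x, CV 40%): +4% to +13%.
- Correlated visit errors (rho 0.3-0.6, same case): -1.0% to -1.3%; from T1 alone, -0.7% to -0.8%.
- Cohort 1: 0.0% to -0.2% at median 30x, but -0.4% to -3.5% at median 6x.

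**Step 5, precision.** The variance of change is 1.5 times the within-subject variance with the two-visit mean and 2.0 times with T1 alone. The ratio of standard errors is sqrt(2/1.5) = 1.155. It is somewhat larger, about 1.2, in Cohort 2, because a selected B1 varies less.

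**The case against.** The strongest reply is that no decision depends on this. The primary endpoint and the 40% rule use absolute targets (SAP 7.5), secondary endpoints have no efficacy targets (Protocol 9.5.1.2), and the SAP calls all summaries exploratory. That stands, and it makes this a minor point.

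Second, SAP 6.3 and 7.6 already point to Visit T1. This stands in part. The wording in 6.3 may be shorthand, since it treats on-site salivary 17-OHP the same way although 3.2.1 prescribes a two-visit mean there too. The documents do not settle which reference applies.

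Third, the shift is small against the noise. With an assumed 10-12 subjects per cohort, the 90% half-width on the log scale runs from 1.796 x 0.3 x sqrt(1.5)/sqrt(12) = 0.19 to 1.833 x 0.5 x sqrt(1.5)/sqrt(10) = 0.36, wider than most of these shifts. True, but a bias moves the point estimate and does not shrink with more subjects.

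Fourth, moving wholesale to T1 would harm one statistic: the arithmetic mean of individual percentages would read +9% to +28% with no effect. This stands and limits the fix.

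A reader might go further and infer that Cohort 2 is bound to show a fall, that only Cohort 2 is affected, or that the 30% rule helps cause it. The documents do not support this. They set a floor of 4x ULN with no ceiling, so closeness to the threshold is an assumption. Cohort 1 faces the same B1 requirement. The stability rule reduces the bias.

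**Conclusion.** The point holds in a limited form. Under SAP 3.2.1 half of the serum 17-OHP baseline normally comes from a value used for entry, and 3.2.1 does not agree with 6.3 and 7.6. Under the Cohort 2 assumptions above, the shift without drug effect is about 0 to -6% of mean baseline. In median percentage change it is -4% to -16%, of which 2-6 points belong to the denominator.

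These sizes rest on within-subject variation and a distance from 4x ULN that the documents do not give. Lower true levels with more variation would enlarge the shift; higher levels, or 17-OHP still rising, would remove or reverse it. Only descriptive summaries of change are touched, and nothing here bears on whether the trial is declared positive.

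**What to change.** By SAP amendment before final database lock:

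1. Make 3.2.1, 6.3 and 7.6 name the same reference for change in serum 17-OHP and for the summed series.
2. Beside the two-visit-mean result, report by cohort the change from the T1 predose value alone, as absolute change and as median or geometric-mean (log-scale) percentage change. Do not report the arithmetic mean of individual percentages from T1. Extend SAP 7.1 to allow geometric means for this table.

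The cost is one derived variable and one extra column, with T1-only intervals about 15-20% wider. T1 alone removes the shift if visit errors are independent; with correlated errors a little remains (under 1% in the case tried).

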9.5.2.2. Exploratory Efficacy Endpoints

Additional efficacy endpoints may be prespecified in the SAP, including sensitivity analyses associated with drug compliance and missing data issues.

9.6. Safety

9.6.1. Safety Endpoints

Safety endpoints include the incidence of treatment-emergent AEs and SAEs, as well as the values and changes from baseline in clinical laboratory tests, vital signs, PEs and ECG parameters. There are no prespecified targets for the safety endpoints.

9.6.2. Safety Analyses

No inferential statistical analyses will be performed on the safety data from this study. The Safety Population will be used for all summaries of safety data. Only observed case data will be used. The summarization of AEs will include treatment-emergent AEs (TEAEs; defined as AEs that begin or worsen after the first dose of study drug). TEAEs and treatment-emergent SAEs (TESAEs) will be summarized by MedDRA system organ class (SOC) and preferred term (PT), severity, and relationship to study drug, overall, by nevanimibe HCl dose, and by cohort. Deaths and discontinuations due to AEs will each be summarized, overall, by nevanimibe HCl dose, and by cohort. Clinical safety laboratory results, PE findings, vital signs, and ECG readings will be summarized by value and by change from baseline in the value, where appropriate, for each time point, overall, by nevanimibe HCl dose, and by cohort using summary statistics for continuous parameters, including number of non-missing observations (n), mean and/or median, standard deviation (SD) and/or percentiles, minimum (min), and maximum (max). Frequencies and percentages as well as shift tables will be prepared for categorical parameters.

9.7. Pharmacokinetics and Pharmacodynamics

9.7.1. Pharmacokinetic and Pharmacodynamic Endpoints

The PK and PD endpoints include the following:

- The C_{\max} , T_{\max} , AUC_{0-4} and other PK parameters of nevanimibe and its major metabolite(s) (as appropriate and as the data allow)
- The relationship between the C_{\max} and AUC_{0-4} of nevanimibe and its major metabolite(s) in relation to the change in 17-OHP levels (as appropriate and as the data allow)

Additional PK and PD endpoints may be described in the SAP.

9.7.2. Pharmacokinetic and Pharmacodynamic Analyses

The analysis of the PK and PD parameters will be performed on the PK Population. PK assessments will be performed at each dose level to determine exposures to nevanimibe and its major metabolite(s) and to profile PK/PD relationships. PK assessments will include C_{\max} , T_{\max} , AUC_{0-4} and trough levels.

Individual subject PK data will be analyzed along with pooling of subjects' data at each dose level. Individual PK parameters will be computed to the extent allowed by the PK data collection times. Tabular summaries will be provided using descriptive summary statistics, including number of non-missing observations (n), arithmetic mean and/or geometric mean and/or median, standard deviation (SD) and/or standard error (SE), minimum (min), and maximum (max). PK/PD analyses will be detailed in the Statistical Analysis Plan.

9.8. Interim Analysis

No interim analysis is planned for this study.

10. ADMINISTRATIVE CONSIDERATIONS

10.1. Institutional Review Board (IRB)/Ethics Committee (EC)

Prior to initiation of the study at each investigational site, the protocol, the informed consent form(s), the subject information sheet(s), details of the subject recruitment procedures and any other relevant study documentation will be submitted to the responsible local and/or central IRB/EC. A letter from the IRB/EC indicating approval of the Investigator and study site must be submitted to the study Sponsor. All reviews and approval by the IRB/EC will be in accordance with Title 21 of the Code of Federal Regulations (CFR), Part 56. Initial IRB/EC approval and all materials approved by the IRB/EC for this study including the subject consent form and recruitment materials must be maintained by the Investigator and made available for inspection.

The Investigator will promptly report any new information that may adversely affect the safety of subjects or the conduct of the study to the IRB/EC. Similarly, the Investigator will submit written summaries of the study status to the IRB/EC annually, or more frequently if requested. Upon completion of the study, the Investigator will provide the IRB/EC with a brief report of the outcome of the study, if required.

10.2. Ethical Conduct of the Study

The guidelines of the World Medical Association Declaration of Helsinki in its revised edition (48th General Assembly, Somerset West, Republic of South Africa, October 1996), the guidelines of ICH GCP (Committee for Proprietary Medicinal Products/ICH/135/95), as well as the demands of national drug and data protection laws and other applicable regulatory requirements, will be strictly followed.

10.3. Subject Information and Consent

The Investigator is responsible for ensuring that subjects do not undergo any study-related examination or activity before giving informed consent. The subject must give written consent after the receipt of detailed information regarding the study. The verbal explanation will cover all the elements specified in the written information provided to the subject. If the written informed consent is provided by the legal guardian because the subject is unable to do so, a written or verbal assent from the subject must also be obtained.

The Investigator will inform the subject of the aims, methods, anticipated benefits and potential hazards of the study, including any discomfort it may entail. The subject must be given every opportunity to clarify any points he/she does not understand and must be provided with more information if requested. At the end of the interview, the subject may be given time to reflect and can request more time if needed. The subject and/or legal guardian will be required to sign and date the informed consent form. After completion, informed consent forms will be kept and archived by the Investigator in the Investigator study file.

It should be emphasized to the subject that he or she is at liberty to either discontinue study drug and/or withdraw consent to participate at any time, without penalty or loss of benefits to which he or she is otherwise entitled. Subjects who refuse to give or withdraw written informed consent may not be included or continued in this study, but this will not affect their subsequent care.

Please refer to Title 21 of the CFR, Part 50 – Protection of Human Subjects for specific details on this regulation.

10.4. Subject Confidentiality

Personal and sensitive data will be treated as confidential. The results of the study will be made available for review by authorized representatives of the Sponsor and/or submitted to the IRB/EC and regulatory authorities.

Prior to any screening procedures being performed, the subject's consent is required for the data to be used for these purposes and to gain direct access to their medical records for data verification purposes. The subject must be assured that their identity will be protected. To facilitate this, a unique identification number will be assigned and it will be used when reporting study-related data.

